**5. Informed Consent Process:**

We will consent mothers who are in preterm labor. After consent forms are reviewed, the families will be asked to participate in the study. Consent will be obtained from the parent/legal guardian by a research nurse or the PI/designee trained in the informed consent process. All conversations related to patient participation/research procedures will be performed in private locations.

**6. Research Procedures:**

Following enrollment and consent at time of delivery the infant will be placed in one of four groups (per the following algorithm)

For the immediate cord clamping groups the obstetrician will clamp the umbilical cord immediately (<10sec) after birth, per standard procedure. For the delayed cord clamping groups the obstetrician will clamp the cord at 45 sec after delivery and hold the infant in a sterile bag (thermoregulatory bag) 10-15in below the mother's introitus at vaginal delivery or at/below the level of incision if a cesarean section is performed. A stopwatch will identify the time when the infants' buttocks are delivered from the vagina or the

uterus (or head if breech); time elapsed will be counted in 10sec intervals for the OB by the investigator. Infants in the DCC group will be placed into a sterile bag to minimize heat loss at the sterile field by the delivery OB. Per standard NICU clinical protocol, infants in the ICC groups will be placed in the thermoregulatory bag once they are placed on the neonatal warming bed.

Infants will be brought to NICU once the infant is determined stable by the neonatal resuscitation team. The enrolled infant will then be cared for in the NICU using standard practices and started on either Indocin 0.1 mg/kg/day for 3 days (Groups C and D) or placebo (Groups A and B), depending on group assignment. Randomization of indomethacin is “blinded” to medical care team (physicians, nurses, clinic personnel). Maternal and infant clinical data and infant blood samples will be collected at specified times for measurement of mechanism-based endpoints. In addition to routine assessment of renal function via standard clinical measures of BUN and creatinine, renal function status will also be monitored by serum Cystatin C levels (0.1mL) at 7 and 30 DOL (these will be considered research measures, since they are not routinely measured in NICU patients). Measurements will be done with ELISA (50uL serum required) at [name]’s research lab. The oxygen saturation (SpO2) of all infants is continuously monitored upon admission to the NICU by a Masimo pulse-oximeter. Monitoring starts right after birth until discharge from the hospital. The SpO2 and heart rate waveforms stored in the Masimo pulse-oximeter will be downloaded for analysis. Some NICU beds have a different pulse oximeter (Nelcore) which does not allow for data downloads. If a patient is admitted to bedspace not equipped with a Masimo pulse oximeter, one will be placed but screen and alarms turned off. This is a minimal risk procedure and of no additional cost to the patient for data consistency purposes. A neonatal sleep study/pneumogram (respiratory inductance plethysmography, high-resolution pulse-oximetry and electrocardiography) will be performed on all subjects who are not intubated or on non-invasive ventilation at 30 and 60 days of life. In case infants remain intubated or on non-invasive respiratory support at 60 (55 – 65) DOL, a pneumogram will be performed as soon as that level of respiratory support is weaned or discontinued. The pneumogram is non-invasive and is of minimal risk to patients. All data collected will be measured/recorded by persons who are essentially ‘blinded’ to the delivery/treatment at birth.

If for any medical reason the bedside/attending Obstetrician or Neonatologist has concerns and wishes to become ‘unblinded’ to the infant’s enrollment, the study participant will be removed from the study. We expect that the only practitioner who is unblinded in the study is the specific Neonatologist at the particular infants’ delivery, who most likely is not performing the daily care for the newborn after admission based on the structure of our delivery room teams and NICU service teams. All study infants will routinely be followed-up at UK NICU Graduate Follow-up Clinic after discharge since these clinicians have the primary responsibilities for this standard clinical service in our institution. Research oversight for neurodevelopmental follow-up will be the responsibility of [name]. The TIMP and Bayley Scales of Infant Development-III (BSID-III) will be administered at 3-4, 6-9, and 18-24 months corrected age; these are the standard follow-up times for collection of such data in our clinic, and the tests proposed has been optimized and defined for these age intervals. All exams will be performed by the same therapist trained in high-risk newborn neurodevelopmental exams to avoid performance biases, and will be blinded to the treatment group. Data will be reviewed quarterly by the research team. Money will be given to families (\$25) for expenses (gas, parking, food) for each of the three follow-up evaluations. Frequent phone contact with project personnel has been another technique successfully used in past research by [name] and colleagues. Project personnel will contact participants every 2 weeks until the first measurement (3-4 months), and then monthly until all measurements are complete for the follow up groups (n=400 completed). Participants will be asked to give multiple phone numbers (work, family, and friends) to make contact more feasible; participants who move or change phone numbers will receive gift certificates (\$25) if they contact research personnel with their new address or phone number. Some attrition (~5%) is anticipated and is built into the sample size calculation.

In summary, a total of 3.7 ml of blood (7 time points during the 0-60 days of life, 0.5mL each, and 2 time points with 0.1ml each), 4 head ultrasound measurements (day of life (DOL) three, first week of life, DOL fourteen and at 30 DOL or later), a head MRI at 38 weeks corrected GA will be obtained from each subject as well as 3 measurements of neurodevelopment (TIMP and Bayley III). Enrolled patients will receive a study number to protect confidentiality of demographic information. Data to be collected is shown on the attached data collection instrument. Only the Co-PIs and study coordinators will know the identities

of the patients and be responsible for the storage of collected data. All data will be de-identified.

Studies shown below are marked as part of standard care or research. The 14 day ultrasound is variable, depending on findings on the 7 day ultrasound. Our standard unit policy is to repeat at 14 days if our routine 7 day ultrasound shows a significant hemorrhage.

Timeline	Procedure	Standard Care	Research
at delivery	umbilical cord blood collection (1-5mL)		X
At admission, 24, 48, & 72hr, Days 7, 30, & 60	blood draw (0.5mL) at each time point	X	
72 hours	head ultrasound		X
7 & 30 days	head ultrasound	X	
7 & 30 days	Serum Cystatin C (0.1mL)		X
14 days	head ultrasound	X	X
Days 30 & 60 if not on vent, or as soon as possible when extubated	neonatal sleep study/pneumogram		X
38 weeks of corrected GA*	head MRI*		X
3-4 months of corrected GA	Test of Infant Motor Performance (TIMP)	X	
6-9 months of corrected GA	Bayley III	X	
18-24 months of corrected GA	Bayley III; Brief infant Toddler Social Emotional Assessment (BITSEA), MCHAT(pass/fail)	X	

\* , Please note that at the initial start of this 5 year study our plan for head MRIs in all enrolled patients is considered a research effort. Note however that the use of head MRI in extremely premature infants that are known to or suspected to have brain lesions is currently common-place and at other institutions is standard care. Therefore it is possible (and perhaps likely) that the routine use of this imaging modality will in coming years become 'standard care' for all preterm infants that are at very high risk of cranial bleeds (e.g. the exact patient group in this study) at our institution. If this becomes the case we will provide amendments to the IRB to account for this issue.

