### 2. Study Design:

***The study design of this research project is a randomized, blinded investigation of 4 treatment groups:***

- 1) Control (no intervention);
- 2) DCC alone;
- 3) Prophylactic indomethacin alone;
- 4) Combination of DCC/indomethacin

Infants randomized to block randomization with blocks of size 8 each to randomly assign the subjects into one of the 4 groups. The randomization table will be prepared in advance by the statistician and clinicians will be blinded to this choice prior to the delivery. Investigational Drug Services will provide indomethacin dosing solutions and placebo dosing solutions that are matched in appearance and volume for each study participant. Please note that randomization will occur in all cases, but the attending Neonatologist at delivery and bedside will have authority to define care; if this physician has an objection to the randomization of indomethacin treatment for a specific patient that patient will be excluded from the study. Similar provisions are afforded to the delivering Obstetrician regarding delay of umbilical cord clamp randomization and treatment.

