**4. Subject Recruitment Methods and Privacy: Recruitment:**

[figure not shown]
A total of 400 premature infants born <29 6/7weeks GA will be recruited from the obstetrics admission area and randomized to one of the 4 treatment groups; n=100 each will complete the study (control; DCC alone; Indomethacin alone; DCC + Indomethacin). This facility admits over 800 sick newborn infants/yr and sees a majority of the high-risk obstetrical patients in the Lexington area and beyond. Informed consent will be obtained prior to patient enrollment, by [name] (PI) or another member of the research team experienced at consenting mothers for research studies. There will also be an on-call schedule at night to screen potentially eligible women, enroll them, and attend the births. Women enrolled will be assigned to either immediate or delayed cord clamping groups via a computer generated random number system to assure permuted block randomization. When notified of a subject's impending birth, the research coordinator will open the randomization card, review the protocol with the attending/fellow/or resident obstetrician, and time the cord clamping.

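### The cord-clamping factor does not have the blind that Sections 2 and 6 state, and no procedure supports the promise that data recorders are blinded to it

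*Combined protocol and SAP*

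**What the plan says.** Section 2 (Study Design) describes a "randomized, blinded investigation of 4 treatment groups" and says that "clinicians will be blinded to this choice prior to the delivery". Matched dosing solutions from Investigational Drug Services mask the indomethacin factor. No masking is described for cord clamping.

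Section 4 (Subject Recruitment Methods and Privacy) says that, on notice of an impending birth, "the research coordinator will open the randomization card, review the protocol with the attending/fellow/or resident obstetrician, and time the cord clamping". In Section 6 (Research Procedures) the obstetrician clamps either within 10 seconds or at 45 seconds, and "time elapsed will be counted in 10sec intervals for the OB by the investigator".

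Section 6 then makes three statements about who is blinded:
- The medical care team is blinded to the indomethacin allocation. This sentence names that factor only.
- "All data collected will be measured/recorded by persons who are essentially" blinded to the delivery and treatment at birth.
- "We expect that the only practitioner who is unblinded in the study is the specific Neonatologist at the particular" infant's delivery, who is thought unlikely to provide the daily care after admission.

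It adds that the follow-up therapist is blinded to treatment group. In its summary of procedures it says: "Only the Co-PIs and study coordinators will know the identities" of the patients, and it makes the same people responsible for storing the data.

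**The concern.** The trial has two factors that differ in what can be masked. A placebo can hide indomethacin. Nothing can hide the timing of clamping from the person who clamps or the person who times it. The plan nevertheless uses one word, blinded, for all four groups and names a single unblinded practitioner.

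Half of the factorial is affected. With 100 infants per group (Section 4), the delayed-against-immediate contrast compares 200 with 200. Under Aim 1 of the statistical analysis plan, the Aim 1B comparison of Groups 3 and 4 (100 with 100) differs only in cord arm. If these contrasts were reported as blinded, readers would credit them with a protection they do not have.

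For the cord contrast, the protection that can be achieved is blinded assessment after delivery. It matters because the primary outcome uses severe IVH and PVL read from head ultrasound and MRI, and because other outcomes, such as pressor support and toxicity, leave room for judgement. The plan promises this protection in one hedged sentence and does not say how it is kept.

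**Working it through.** No arithmetic applies beyond the group totals. The check takes each role in turn and asks whether the procedures let that person know the cord arm, and what the plan says that person does with data.

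| Role | Knows the cord arm? | Data role stated |
|---|---|---|
| Obstetrician | Yes: briefed once the card is open (Section 4), performs the clamping (Section 6) | None |
| Delivery neonatologist | Yes: acknowledged in Section 6 | None; daily care thought unlikely |
| Research coordinator | Yes: opens the card and times the clamping (Section 4) | Knows identities, stores data (Section 6) |
| Timing investigator | Yes: counts for the obstetrician (Section 6) | None, unless also a Co-PI, which is not stated |
| Data recorders | Essentially blinded (Section 6) | Measure and record; not named |
| Ultrasound and MRI readers | Covered only by the general sentence on recorders | Not named |
| Follow-up therapist | Blinded (Section 6) | Developmental testing |

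1. **The claim of a single unblinded practitioner.** The obstetrician is plainly a practitioner and plainly knows the cord arm, so the claim fails for this factor on that role alone. The coordinator also knows it. The coordinator of Section 4 and the investigator of Section 6 are both described as timing the clamping and may be one person. The secure count is therefore at least two roles besides the neonatologist.

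2. **Other signals in the delivery room.** Under Section 6, delayed-clamping infants go into the thermal bag at the sterile field and immediate-clamping infants on the warming bed. Staff present can see which.

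3. **The pre-delivery blind.** Section 2 blinds clinicians until delivery. Section 4 opens the card when birth is impending and has the coordinator go through the protocol with the obstetrician. These need reconciling for the cord arm.

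4. **The unblinding rule.** Section 6 removes a participant if the obstetrician or neonatologist asks to be unblinded. For the cord factor the obstetrician already knows, so the rule makes sense only for the drug.

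5. **Objections and exclusions.** In Section 2 a patient is excluded "if this physician has an objection to the randomization of indomethacin treatment for a specific patient", with similar provisions for the obstetrician on cord clamping. The text does not say whether this happens before or after the card is opened. If after, an infant could be excluded with the cord arm known, which could affect the comparison even with perfectly blinded readers.

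6. **Blinded recording.** The coordinator role joins knowledge of the cord arm to knowledge of identities and custody of the data. The on-call team of Section 4 also attends births, and the research team reviews data quarterly (Section 6). Nothing in the text separates those who learned the arm from those who link, abstract or code the same infant's data.

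**The case against.** The strongest reply is that the plan already has the protections that matter. Clamping cannot be hidden from those who do it, and the hedge in the sentence on recorders admits as much. The sentence on the neonatologist is about carry-over into NICU care, and the obstetrician has no stated role there or in outcome assessment. Recorders and the therapist are described as blinded, and participants carry study numbers. Storing data is not recording it.

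Much of this stands. The summary in Section 6 gives coordinators identities and storage, and no sentence has them measure or judge outcomes. A reader might infer that unblinded staff are shown to record outcomes; the documents do not show this.

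A reader might also infer that opening the card exposes the drug arm, because Section 2 uses one list of four groups and Section 6 places the infant in one of four at delivery. The documents do not show what is on the card. Section 4 ties the assignment to immediate or delayed clamping, which points to a card showing the cord arm only, and the algorithm that Section 6 refers to does not appear in the text available. Nor does the neonatologist's right to object contradict the drug blind. It reads naturally as an objection to that infant being randomized to indomethacin or placebo at all, which requires no knowledge of the allocation.

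The reply does not rescue the unqualified description in Section 2 or the single-practitioner sentence. It also supplies no procedure behind the promise of blinded recording.

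**Conclusion.** The point holds in a limited form. The stated blind is wrong for cord clamping: the obstetrician and the coordinator know the cord arm under the plan's own procedure, for all 400 planned infants, in addition to the neonatologist whom the plan acknowledges. This rests on the text alone. The promise of blinded recording is unsupported rather than contradicted, and the coordinator's combined knowledge of arm, identity and data custody is a risk to it. The size of any resulting bias cannot be derived from the documents.

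The documents do not support concluding that outcome recording was unblinded or that the drug blind fails in the delivery room. The matched placebo and the stated care-team blind for indomethacin stand. The plan should be changed, because it claims a property that one factor lacks and the remedy is cheap.

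**What to change.** 1. In Sections 2 and 6, state the blind by factor: cord clamping open to delivery-room staff with blinded outcome assessment; indomethacin against placebo double-blind. Limit the unblinding rule and the single-practitioner sentence accordingly.
2. In Sections 4 and 6, add a duty rule: whoever opened the card, timed the clamping or attended the birth does not abstract or code that infant's clinical, imaging or toxicity data. Another member of the existing team does. State who reads the ultrasound and MRI, and that they read under study number without cord-arm information.
3. State in Section 4 that the delivery card shows only the cord arm, as that section implies. Reconcile Sections 4 and 6 on who times the clamping.
4. Reconcile Sections 2, 4 and 6 on when a physician's objection or an exclusion occurs relative to opening the card. This asks only for the sequence to be stated and recorded; physician authority is unchanged.

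The cost is protocol wording, a statement of what the card shows and some scheduling burden on the on-call team. Sample size and treatment do not change. The cord comparison, including Aim 1B, can then no longer be reported as fully blinded.

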## Study Protocol:

### 1. Objectives:

**Primary GOAL:** Compare efficacy and safety of prophylactic indomethacin, DCC, and their combination, in affecting the incidence and severity of IVH in infants less than 29wks GA at birth.

- **Aim 1A):** Test for differences in primary outcome measure: 'fraction of survivors with no severe IVH or PVL' among the 4 groups, using head ultrasound (1-30d), and head MRI at 38wks adjusted GA.
- **Aim 1B):** Test the hypothesis that DCC improves effectiveness and/or decreases toxicities of indomethacin.
- **Aim 1C):** Test for treatment dependent differences in neurocognitive follow up evaluations and investigate relationships between short term brain imaging results and later neurocognitive performance across treatment groups.

**Secondary GOAL:** Investigate mechanistic effects of prophylactic indomethacin, DCC, and their combination in infants less than 29wks GA.

- **Aim 2A):** Test the hypotheses that blood volume status and/or hemodynamic stability are different between groups (at 0,1,2,3,7, 30, and 60 days of life).
- **Aim 2B):** Test the hypothesis that biomarkers of inflammation and vascular endothelial stress are different between groups (at 0,1,2,3,7, 30, and 60 days of life).
- **Aim 2C):** Test the hypothesis that numbers, or apoptotic frequency, of circulating progenitor cells with endothelial or neuronal phenotype capacity are different between groups (at 0,1,2,3,7, 30 and 60 days of life).
- **Aim 3):** Determine relationships between clinical outcomes (Aim1) and blood measurements (Aim 2) among treatment groups.

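### No by-arm review of deaths and no harm rule is pre-specified, and the plan does not say that deaths are still collected for infants removed from the study

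*Combined protocol and SAP*

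**What the plan says.** Section 1 (Objectives) gives the primary goal as "Compare efficacy and safety of prophylactic indomethacin, DCC, and their combination". Section 4 plans four arms, of which "n=100 each will complete the study". Section 3 plans 400 infants enrolled from July 2014 to June 2019.

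The one periodic review is in Section 6: "Data will be reviewed quarterly by the research team". It stands among the sentences on the TIMP and Bayley follow-up visits, and nothing more is said about what the review covers.

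The other safeguards act on one infant at a time:
- Section 2 lets the neonatologist or obstetrician object to an assignment. For indomethacin, the infant is then excluded.
- Section 6 says that "renal function status will also be monitored by serum Cystatin C levels", alongside routine BUN and creatinine, with no trigger at arm level.
- Section 6 also says that if a physician has concerns and wants to be unblinded, "the study participant will be removed from the study".

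Indomethacin assignment is masked to the care team (Section 6). The SAP text for Aim 1 compares renal status, comorbidities and hospital stay across the four groups, without interim timing. It describes the analyses as intention to treat where that is appropriate.

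**The concern.** Death counts against the primary outcome, which is survival without severe IVH or PVL. If indomethacin, delayed clamping or one combination raised mortality, the planned safeguards would not show it as a difference between arms. Clinicians masked to the drug cannot compare deaths by drug, and excluding or removing single infants does not lead to a comparison. Whether the quarterly review would reveal the difference depends on content that the plan does not state.

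The removal rule adds a second problem. Infants whose physicians are worried enough to ask for unblinding may well be the sickest. If follow-up stops at removal, deaths are lost in a way related to outcome, which weakens both the safety comparison and the primary analysis.

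**Working it through.** **What the text contains.** I looked through Sections 1 to 6 and the SAP for a monitoring committee, an interim look, a harm threshold, a pause rule or an adverse-event reporting rule. None appears. The IRB is mentioned once, about head MRI becoming standard care: "we will provide amendments to the IRB to account for this issue".

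**Exposure, from the plan's own figures.** 400/4 = 100 per arm, as stated. 400/2 = 200 at each level of each factor. July 2014 to June 2019 is 60 months or 20 quarters, so 400/20 = 20 infants per quarter (5 per arm) if enrolment is even.

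**What a harm rule could do.** The plan gives no death rates, so every rate below is an assumption. The example rule looks after quarters 1 to 19 and uses the pooled two-proportion statistic

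z = (d1/n − d0/n) / √[p(1−p)·2/n], with p = (d1+d0)/(2n).

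A comparison crosses at one-sided p<0.005 (z above 2.576) with at least 10 deaths in it, and a pause is treated as a stop. Each scenario used 100,000 simulated trials.

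With no rule, excess deaths are 200 × (rate difference), for example 200 × 0.15 = 30. Excess deaths avoided are (400 − mean enrolled)/2 × (rate difference), for example (400 − 202)/2 × 0.15 ≈ 14.9.

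Harm from a whole factor (200 v 200, that comparison only):

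| Assumed death rates | Caught, deaths known at once | Caught, one-quarter lag | Mean enrolled, no lag | Excess deaths avoided, no lag |
|---|---|---|---|---|
| 15% v 30% | 88.2% | 86.2% | 202 | 14.9 of 30 |
| 20% v 35% | 83.2% | 80.8% | 219 | 13.6 of 30 |
| 25% v 40% | 79.3% | 76.7% | 231 | 12.7 of 30 |
| 10% v 20% | 66.5% | 63.7% | 271 | 6.4 of 20 |
| 15% v 25% | 56.1% | 53.6% | 292 | 5.4 of 20 |
| 15% v 20% | 18.0% | 17.0% | 366 | 0.9 of 10 |

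Harm in one arm only (15% to 30%, no lag), by the comparisons monitored:

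| Harmful arm | Two factors + combination v control | Plus indomethacin alone v control | Plus DCC alone v control |
|---|---|---|---|
| Indomethacin alone | 34.6% | 61.0% | 61.1% |
| DCC alone | 35.0% | 36.1% | 61.2% |
| Combination | 64.6% | 64.7% | 64.7% |

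Each single-treatment arm therefore needs its own comparison with control. Aim 1B supposes that DCC may lessen indomethacin toxicity, so harm concentrated in indomethacin alone is a pattern that the plan itself anticipates.

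**False pauses with no true harm, all five comparisons.** At p<0.005: 7.1% with 15% deaths (5.9% at 10%, 9.0% at 25%). At p<0.00135 (z above 3.0): 2.2% (1.7% to 3.0%). The stricter boundary costs detection: 15% v 30% falls to 76.6%, 10% v 20% to 48.6%, and 15% v 25% to 37.8%. For indomethacin alone it is 41.6% with four comparisons.

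**A different rule.** Looks at 100, 200 and 300 infants with z of at least 2.0 on a factor comparison pause 90% of trials at 15% v 30% and 72% at 10% v 20%. The benefit does not depend on one boundary.

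**The case against.** The strongest reply is that this argues from absence in a partial text. The numbered sections stop at 6. Attrition "is anticipated and is built into the sample size calculation", but that calculation is not in the document, and neither is the attached data collection instrument. A monitoring section could be absent for the same reason. This stands, and it limits the point to asking the sponsor to state or cite the plan.

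A reader might infer that nothing at all would prompt a pause. The documents do not support that: a quarterly review is planned, and its place among the follow-up sentences suggests a narrow scope without proving that deaths are left out. Cord clamping is also known to the delivering obstetrician and the delivery-room neonatologist, so the masking argument applies to the drug only. Nor can one infer that removed infants are dropped from the analysis, because the intention-to-treat wording points the other way. What is missing is a statement that their deaths are collected.

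The benefit is also easy to oversell. The 88% applies to a whole-factor doubling from 15%, and results move with the assumed rate. The exclusions could make mortality lower than tested above: at an assumed 5%, the same rule catches 5% v 15% in 83% of trials but a doubling to 10% in only 33%. The number of looks, the boundary and the minimum death count are one reasonable choice among several. The rule covers deaths only, so severe IVH and renal toxicity would still have no trigger.

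**Conclusion.** The point holds for what is pre-specified: no by-arm review of deaths, no harm rule, and no statement that deaths after removal are collected. It does not show that the trial ran without safety oversight.

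An added rule would usually detect a large whole-factor rise in deaths, at a median of 160 infants among the trials that cross for 15% v 30%. It is much less reliable for harm in a single arm and of little use against a 5-point rise. These figures rest on assumed death rates, even enrolment of 20 infants per quarter, and a pause that becomes a stop. The case for the change rests on its low cost and on the gap in the text, not on a precise count of deaths avoided. It is a worthwhile improvement, held with medium confidence because a separate monitoring plan may exist.

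**What to change.** 1. State that every randomized infant, including those removed after a request for unblinding, stays in outcome collection, at least for death. This fits the intention-to-treat wording of the SAP.

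2. If a monitoring plan already covers deaths by arm, cite it. If not, add a quarterly by-arm death table with five comparisons: indomethacin v placebo, DCC v immediate clamping, and each of the three active arms v control. Attach a harm-only trigger, for example one-sided p<0.005 with at least 10 deaths in the comparison, or p<0.00135 if fewer false pauses are wanted; the sponsor may choose another. Crossing it pauses enrolment and sends the unblinded table to the IRB or another body independent of the research team, which decides what follows. The rest of the team stays masked to deaths by arm.

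The table should come from an existing trial statistician. Section 2 says "The randomization table will be prepared in advance by the statistician and clinicians will be blinded to this choice prior to the delivery", so access to assignments fits that role. Because the SAP selects covariates from the data and death is part of the primary outcome, this person must take no part in covariate selection. The SAP names two analysis leads, so the tasks could be divided between them, but the arrangement has to be written down.

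Cost: a short amendment and one table per quarter, with no additional infants and no efficacy alpha spent, because the look is for harm only. The downsides are the false-pause rate shown above, one statistician who sees deaths by arm, and the need for the receiving body to agree to the role.

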### 3. Study Population:

It is anticipated that this study will begin July, 2014 and will enroll subjects through June 31 of 2019. Follow-up in NICU Graduate Clinic will continue thru June 31, 2020. We are going to enroll 400 infants during that time, male and female all inborn at the University of Kentucky. The population is primarily Caucasian (80%), African American (15%), Asian (3%), and a Hispanic population of about 2%. All races and ethnicities will be included if subjects parent(s) are able to understand English (spoken or written). Pregnant women are considered to also be research subjects in this trial. When the pregnant mother is a

legal adult (18yrs or older) their consent will include their participation as well as their infant. Pregnant women whom are less than 18yrs and greater than 14yrs of age and qualify for enrollment criteria will also be invited to participate in this study. In these cases assent will be obtained from the pregnant mother (who is considered a legal minor), and consent will be obtained from the pregnant mother's legal guardian.

Inclusion criteria

- Neonates with a GA less than 29 6/7weeks (based on last menstrual period and/or early pregnancy ultrasound)
- Consent obtained prior to delivery

Exclusion criteria

- neonates with congenital anomalies such as congenital heart disease
- a prenatal plan to withhold neonatal care
- maternal risks identified by obstetrician, including severe hemorrhage (placenta abruption or placental previa), hypertensive crisis
- if the attending obstetrician or neonatologist decides that infant requires immediate resuscitation for either maternal or newborn well-being
- any prenatal indocin use within 72 hours before birth

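### Randomising 400 infants, losing about 5% and having 400 complete cannot all be true; with enrolment at 400, about 380 (95 per arm) complete follow-up before deaths are counted.

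*Combined protocol and SAP*

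**What the plan says.** Section 3 (Study Population) gives the enrolment target: "We are going to enroll 400 infants during that time". Section 4 (Subject Recruitment Methods and Privacy) uses the same 400 for the number recruited and randomised, and in the same sentence gives the completers: "randomized to one of the 4 treatment groups; n=100 each will complete the study". Four arms of 100 make 400.

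Section 6 (Research Procedures) repeats that total when it describes how families will be contacted: "until all measurements are complete for the follow up groups (n=400 completed". Shortly after, it states the allowance for loss: "Some attrition (~5%) is anticipated and is built into the sample size calculation".

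No section gives a recruitment figure above 400, a completer figure below 400, or a rule for replacing infants who are lost. The calculation said to contain the 5% is not shown. The Aim 3 part of the statistical analysis plan says only that the study was powered with chi-square tests for equality of proportions, without rates, effect size or power.

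**The concern.** If 400 infants are randomised and 400 complete, nobody is lost. Yet the plan expects to lose about one infant in twenty and says that this is already covered. A reader will conclude both that an allowance exists and that 100 infants per arm will be available at the end; the stated numbers do not allow both.

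The figure at stake is the sample for Aim 1C: the neurodevelopmental assessments, the last at 18-24 months corrected age, and their relation to early brain imaging. Any detectable difference or interval width worked out from 100 per arm would rest on more infants than the design delivers. Deaths add to this. The primary outcome is defined on survival, so the plan itself expects some, and an infant who has died cannot be tested at 18-24 months.

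**Working it through.** **Inputs from the documents**

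- Enrolled and randomised: 400 (sections 3 and 4).
- Completers: 100 per arm, 400 in total (sections 4 and 6).
- Attrition: about 5% (section 6).
- Allocation: blocks of 8 over four groups (section 2). Equal allocation is inferred from the 100 per arm.

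**Step 1. Does the stated completer count follow?** Completers = N x (1 - d), with N = 400 and d = 0.05.

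- Total: 400 x 0.95 = 380. Per arm: 380 / 4 = 95.
- The stated figures are 400 and 100, so the shortfall is 20 infants, or 5 per arm. The plan's figure is not reproduced.
- Reading the approximate 5% as 4% to 6% gives 400 x 0.96 = 384 to 400 x 0.94 = 376. Neither is close to 400.

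**Step 2. How many must be randomised for 400 to complete?** N = completers / (1 - d).

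- 400 / 0.95 = 421.05, rounded up to 422.
- With equal arms: 100 / 0.95 = 105.3, rounded up to 106 per arm, or 424. This is also a whole number of blocks (424 / 8 = 53).
- The cruder formula N x (1 + d) gives 400 x 1.05 = 420, which also exceeds 400.

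**Step 3. Could 400 already include the allowance?** 380 / 0.95 = 400 exactly. It could, but only if the completer target is 380.

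**Step 4. Losses beyond the 5%.** The documents give no mortality. As an assumption, let a proportion m die and let the 5% apply to survivors: completers = 400 x (1 - m) x 0.95.

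| Assumed m | Completers | Per arm |
|---|---|---|
| 5% | 361 | 90 |
| 10% | 342 | 86 |
| 15% | 323 | 81 |
| 20% | 304 | 76 |

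(Per-arm figures are rounded.) The plan names two further routes out. Under section 2, an infant is excluded if the responsible physician objects to the assignment. Under section 6, if a treating physician asks to be unblinded, "the study participant will be removed from the study". Neither has a stated rate, so neither is in the table.

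**Step 5. What this does to a two-arm comparison.** The plan states no detectable difference for Aim 1C. For illustration, take a continuous score, two-sided alpha 0.05 and 80% power (both assumed): difference in SD units = 2.80 x sqrt(2/n).

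- n = 100: 0.396, or 0.40 SD.
- n = 95: 0.406, or 0.41 SD.
- n = 76 (only with the assumed 20% mortality): 0.454, or 0.45 SD.

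For a binary outcome under assumed rates, moving from 100 to 95 per arm costs about 2 points of power: 0.876 to 0.859 for 60% against 80%, and 0.722 to 0.700 for 70% against 85%.

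**The case against.** The strongest defence is that 400 is the inflated number. The plan says that attrition is built in, the calculation is not available to check, and 380 / 0.95 comes to exactly 400. This stands as far as it goes. A reader might infer that no allowance for attrition was made; the documents do not support that, because 400 randomised with a target of 380 fits the statement about attrition. The defence does not rescue the text, however: if 400 is the inflated figure, both completer statements are wrong.

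The opposite defence is that 400 is the completer target. Then the enrolment figure in sections 3 and 4 is too low by 22 to 24. No larger figure appears anywhere, and enrolment at 400 is stated twice, which favours the first reading without proving it.

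A reader might also infer that the plan overstates its precision. The documents give no power, interval width or detectable difference for Aim 1C, so only a stated sample size is too high.

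It can also be said that the matter is minor. That is largely right. The documented 5% moves the illustrative detectable difference by about 0.01 SD, and the larger figures depend on a mortality the documents do not give. Finally, the 5% sits in text about keeping families in follow-up. It does not show a 5% loss for the primary outcome, which rests on ultrasound in the first 30 days and MRI at 38 weeks.

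**Conclusion.** The inconsistency is real and follows from the plan's own figures. Taking enrolment as 400, the completer count is about 20 too high: 380 rather than 400, 95 rather than 100 per arm. The documents do not show which of the conflicting figures the sponsor would keep.

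The figure of 380 is itself an upper bound if the 5% covers only families lost to follow-up, because deaths and removals come on top. The range of 361 to 304 illustrates this under an assumed mortality of 5-20%, applied before the 5%; it is not an estimate for this trial. The consequence of the 5% alone is small and confined to Aim 1C. It is worth correcting because the plan tells readers that attrition is covered while also promising as many completers as infants randomised.

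**What to change.** Keep 400 as the number randomised. In section 4 replace "n=100 each will complete the study", and in section 6 replace the statement that 400 complete, with about 380 (95 per arm) before deaths. Then state three numbers separately: infants randomised, infants evaluable for the primary outcome, and infants expected at 18-24 months after deaths, removals following unblinding and exclusions on physician objection, with the rates assumed for each. Show the sample size calculation and where the 5% enters it. Base any detectable difference given for Aim 1C on the restated follow-up number.

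This costs wording only and enrols no more infants; the stated follow-up sample becomes somewhat less favourable. If the calculation, once shown, turns out to require 100 completers per arm, the sponsor would have to choose between accepting about 95 and randomising 22 to 24 more.
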